1.3 REVIEW OF RELEVANT EXISTING EVIDENCE

As noted above recent SRs and meta-analyses (MAs) conclude that overall effects on *mortality* are similar between restrictive and liberal RBC transfusion strategies²⁶ ³⁵, but no studies were conducted specifically in our study population. Importantly, heterogeneity of effects are emerging from recent SRs/MAs restricted to populations with co-morbidities²⁷ ²⁸. Two ICU based transfusion trials measured HRQoL: a trial in septic shock patients³⁶, and our trial in older patients requiring prolonged mechanical ventilation³⁷. The intervention in both trials occurred during ICU, and ICU mortality was high. Survivor cohorts were small, confirmed markedly reduced HRQoL, but found no differences in HRQoL. In addition to limited statistical power, these analyses did not adjust for baseline health status or other factors, which we and others have shown to be important determinants of HRQoL in heterogeneous ICU populations³⁸ ³⁹. No rehabilitation trials have considered anaemia treatment either as the main intervention or as part of the intervention.²³

A large observational literature demonstrates the high disability burden suffered by ICU survivors, especially during the first 3-6 months, but often lasting many years. This includes physical impairments, reduced Activities of Daily Living (ADLs), and mental and cognitive disability. ^{1 3 40} Pre-existing health status is an important determinant of post-ICU disability, but has not been widely considered in published trials, which may explain in part why the increasing number of ICU rehabilitation trials have demonstrated disappointing effects on outcomes.

1.4 RATIONALE FOR STUDY

1.4.1 Research Questions:

- Does correcting anaemia using blood transfusions improve patients' quality of life, fatigue, disability, cardiac complications, and survival after being discharged from intensive care?
- Does correcting anaemia using blood transfusions reduce the time needed in hospital after being discharged from intensive care?
- Is correcting anaemia using blood transfusions a cost-effective treatment after being discharged from intensive care?
- Are there certain groups of intensive care survivors who benefit more from correcting anaemia using blood transfusions?

1.4.2 Hypothesis:

In patients discharged from intensive care with moderate to severe anaemia, correction of anaemia using blood transfusions will improve quality of life, disability, and other measures of well-being

2 STUDY OBJECTIVES

2.1 PRIMARY OBJECTIVE

To determine whether correcting anaemia from the time of ICU discharge using blood transfusions (target Hb 100-120g/L) results in an improvement in self-reported quality of life (HRQoL) 90 days after intensive care discharge, compared with current usual care which recommends transfusions when Hb is less than 70g/L to achieve a target Hb 70-90g/L.

2.2 SECONDARY OBJECTIVES

- To determine the effect of correcting anaemia using blood transfusions on fatigue, disability, and death rate compared with current usual care
- To determine the safety of correcting anaemia with blood transfusions, compared with current usual care
- To determine which patients may benefit most from more active correction of anaemia using blood transfusions
- To determine whether more active correction of anaemia using blood transfusions is cost-effective in the NHS

2.3 ENDPOINTS

2.3.1 Primary Endpoint/Outcome

Physical Component Score (PCS) of the SF-36 HRQoL questionnaire at 90 days post-randomisation.

2.3.2 Secondary Endpoints/Outcomes

Patient centred outcomes:

- 1. Physical Component Score (PCS) of the SF-36 HRQoL questionnaire (and its four sub-domains) at 30 and 90 days post-randomisation.
- 2. Patient fatigue (Fatigue Severity Scale (FSS)) at 30, 90 and 180 days post-randomisation
- 3. Mental component score SF-36 (and its four sub-domains) at 30, 90 and 180 days post-randomisation.
- 4. Activities of Daily Living (ADLs) (WHODAS questionnaire⁴) at 90 days post-randomisation
- 5. Patients alive at 30, 90 and 180 days post-randomisation
- 6. Patients alive at 5 years post-randomisation derived from data linkage
- 7. Haemoglobin concentration at 30 days post-randomisation

Resource use and cost-effectiveness (based on data linkage and questionnaires):

- 8. Post-ICU length of hospital stay;
- 9. Care costs during 180 days post-randomisation.

- 10. Incremental cost per QALY at 180 days
- 11. Care costs derived from data linkage during 5 years post-randomisation (depending on results from shorter term outcome analysis)

Process and Safety outcomes:

- 12. Protocol compliance (during intervention index hospital stay)
- 13. Hb concentration (during index hospital stay)
- 14. RBC use (during 90 days follow up)
- 15. New Infections (during 90 days follow-up)
- 16. Transfusion-related adverse events (during 90 days follow-up)
- 17. Major adverse cardiovascular events (MACE; during 90 days follow-up)

3 STUDY DESIGN

3.1 STUDY DESIGN OVERVIEW

We propose a prospective, parallel group, randomised controlled intervention trial.

3.1.1 Personalised Medicine

We recognise the need for *personalised medicine*, especially in relation to the use of blood transfusions, and will use novel approaches to explore two key issues that will inform which patients may gain greatest benefit from this intervention:

Prediction (moderation) variables (what baseline covariates influence treatment success): the importance of baseline co-morbidity, HRQoL, mobility and/or baseline severity of systemic inflammation (based on C Reactive Protein) will be studied within the trial, and a prediction model developed to help identify who will or will not benefit from blood transfusions.

Mediation variables (what variables measured early after randomisation are on the causal pathway for clinical benefit):

the importance of *systemic inflammation* and *impaired erythrogenesis* post-ICU will be studied within the trial to improve our understanding of the causal pathway whereby transfusions may improve recovery.

These variables may be useful to identify if treatments were working, as surrogate outcomes, or to assist clinical decision-making.

3.2 STUDY SETTING

Acute hospitals managing patients discharged after a period in intensive care

3.3 RESEARCH QUESTIONS

3.3.1 'PICO' research guestion:

Population: ICU survivors with moderate-severe anaemia (WHO definition; Hb≤94g/L). Intervention: RBC transfusion practice to maintain Hb at 100-120g/L during subsequent hospital stay; transfusion trigger <100g/L

Comparator: Current usual RBC transfusion practice to maintain Hb 70-90g/L; transfusion trigger <70g/L

Primary Outcome: Physical Component Score (PCS) of the SF-36 HRQoL questionnaire 90 days post-randomisation

Secondary Outcomes:

To determine whether the intervention improves: Patient fatigue; Patient disability (function and activities of daily living (ADLs)); Rates of major adverse cardiac events (MACE); Survival (up to 5 years); Health service resource use and costs (up to 5 years – according to results of the shorter term outcomes).

To evaluate if the intervention is cost-effective.

3.3.2 Personalised medicine questions:

To explore whether any of the following modify the efficacy of the intervention:

Prediction variables (moderation analyses) – baseline predictive factors

- 1. Pre-existing HRQoL
- 2. Pre-existing co-morbidities
- 3. Mobility status at ICU discharge
- 4. Baseline severity of inflammation (based on C Reactive Protein concentration)

Mechanistic factors (mediation analyses) – post ICU causal mediating factors:

- 5. Persisting systemic inflammation
- 6. Evidence of impaired erythrogenesis

3.3.3 Cost effectiveness questions:

We will estimate cost per life-year and cost per Quality-Adjusted Life Year (QALY) over the follow-up period of the study. Health service costs will rely on patient questionnaires. Depending on the results of the short-term outcomes, linkage of routinely collected healthcare data, including inpatient, outpatient, A&E, and unscheduled care may be undertaken.

4 STUDY POPULATION

4.1 NUMBER OF PARTICIPANTS

The total sample size is 346, allocated 1:1 between the two randomised groups.

We anticipate recruitment will take place in 20-25 sites UK-wide, but more sites will be included according to interest, resources, and recruitment rates. Sites outside the UK will be considered if feasible.

4.2 INCLUSION CRITERIA

- [1] Patient who received level 3 ICU care at any time point during the current hospital admission (defined as advanced respiratory support and/or at least two organ support)
- [2] Patient considered ready for discharge from the ICU by the caring clinical team
- [3] Hb≤94g/L when ready for ICU discharge or during the first seven days following the decision by the treating clinician that the patient is **ready for** ICU discharge
- [4] Age ≥16 years.
- [5] Patient expected to remain in study hospital until hospital discharge

[6] Consent provided (by participant or in accordance with appropriate mental capacity legislation for the site)

4.3 EXCLUSION CRITERIA

- [1] Contraindication or objection to RBC transfusion
- [2] Active bleeding when screened
- [3] Primary neurological ICU admission diagnosis, including primary brain or spinal cord injury
- [4] Patients discharged from the ICU following cardiac surgery
- [5] Currently receiving or planned to receive end-of-life care
- [6] Not expected by clinical team to survive to hospital discharge.
- [7] Patient with a proven chronic haematological disease that requires regular RBC transfusion to treat anaemia
- [8] Patient with dialysis-dependent chronic renal failure prior to ICU admission
- [9] Patient receiving regular erthyropoietin (or any erythropoiesis stimulating agent) treatment for anaemia prior to ICU admission.
- [10] Unable to obtain consent (from patient or in accordance with appropriate mental capacity legislation for the site)
- [11] Readmission to ICU during current hospitalisation episode and not enrolled following previous ICU admissions
- [12] Patient recovering following liver transplantation, kidney transplantation, or combined kidney/pancreas transplantation
- [13] Patient recovering from variceal bleeding due to chronic liver disease
- [14] Prisoners
- [15] Patient due for imminent hospital discharge within the next 24 hours

4.4 CO-ENROLMENT

Co-enrolment will be permitted to other studies and trials once the following criteria and steps have been taken:

- Consideration has been made by both study Chief Investigators of issues related to study design and statistical considerations; legal and ethical considerations; biological and scientific rationale; participant considerations and; logistical and organisational issues.
- Ethical approvals for both studies, and sponsor policies for each study, allow coenrolment
- Agreement to co-enrolment has been documented according to the policies and procedures of both sponsors
- For ACCORD, this is set out in the ACCORD Co-enrolment Policy (POL008 Co-enrolment Policy).

5 PARTICIPANT SELECTION AND ENROLMENT

5.1 IDENTIFYING PARTICIPANTS

5.1.1 Screening

Patients will be screened at the time they are considered ready for ICU discharge by the clinical teams. According to local site arrangements, screening may be undertaken by the ICU clinical teams or ICU rehabilitation teams, in collaboration with research teams or other team members delegated at the local site. Members of the responsible clinical team (which could be the ICU team or ward-based team according to timing) will be asked to confirm suitability prior to any approach for consent.

Screening (and recruitment) can continue for up to seven days following ICU discharge or the patient being considered ready for discharge, whichever occurs first (the recruitment window).

All eligible patients identified from screening will be entered into the screening log, which will be kept in the Investigator Site File (ISF). The screening log, and the outcome of screening for eligible patients, will be completed and maintained by an appropriately trained member of the research team.

5.1.2 Eligibility period

The eligibility window will be from the time the patient meets inclusion criteria and has no exclusion criteria for up to seven days following the decision by the treating clinician that the patient is **ready for ICU discharge**, as long as the patient remains in the acute hospital. The aim will be for enrolment to occur as close to ICU discharge as possible, but recognises that patients are often fatigued and/or may need time to consider participation during this period.

5.1.3 Haemoglobin concentrations during screening and eligibility period

A patient can be screened as eligible for the trial based on any haemoglobin concentration during the eligibility period. If a haemoglobin concentration of 94g/L or less has been measured, and other inclusions/exclusions make the patient eligible, they can be approached for consent. Several scenarios based on the haemoglobin concentration may occur:

- a. The patient provides consent without any further haemoglobin measurement being undertaken for clinical or other reasons. In this situation the patient should be immediately randomised and managed according to the allocated group. There is no requirement to wait for the result of the baseline blood sample Hb measurement or any other Hb measurements before transfusing according to the protocol because the patient has demonstrated eligibility during the eligibility period.
- b. If the patient has been randomised, baseline blood samples have been taken, and the baseline or another Hb measurement becomes available before any transfusion has occurred, transfusion decisions should follow the protocol and group allocation using the most recent Hb concentration. The patient should remain in the trial once randomised and not be withdrawn if the Hb concentration is above 94 g/L on repeat Hb measurement. Transfusions should follow the protocol according to the most recent Hb measurement: for example if the Hb has increased on the baseline blood and is 94-99 g/L the patient should receive 1 unit of RBC if they are in the liberal group, with a target Hb of 100-120g/L. If they are in the restrictive group their Hb should simply be monitored, but they should not be withdrawn.
- c. If a patient is being screened and fulfils all eligibility and no exclusion criteria, *but has not yet provided consent* (for example lack of capacity or patient/family are still considering taking part) the following should guide participation:

- i. If a further Hb concentration is taken for clinical reasons *prior to consent* being obtained, and the result is >94 g/L, the patient is no longer eligible for the trial at that time.
- ii. If after (i) above, a further Hb concentration is taken for clinical or other reasons and is again ≤94 g/L the patient is again eligible if within the 7 days recruitment window. They can then be approached for consent.
- iii. Once a patient has provided consent they should be randomised immediately without waiting for further testing. Once randomised they should remain in the trial as per scenario (a) and (b) above.

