7 DATA COLLECTION

7.1 Definition of time periods

Baseline is the day of randomisation until 23:59 that calendar day.

Study day 1 is the first calendar day after baseline from 00:00 to 23:59. All subsequent study days will follow accordingly.

Study day period is 00:00 to 23:59.

For the purpose of baseline data collection, all data will be extracted from the patient record and apply to the time leading up to randomisation (see details below)

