7.2 Baseline

The following data will be collected:

Demographics: age, sex
Pre-existing health status:

- recalled SF-36 (PCS and MCS) 30 days prior to hospitalisation. Attempt to complete as close to the time of enrolment as possible. For patients lacking capacity at enrolment, this measure can be deferred until patients regain capacity
- Functional Co-morbidity Index (FCI)
- Clinical Frailty Index prior to the onset of the acute illness that resulted in this hospitalisation
- ICU Mobility Scale (IMS) at the time of randomisation
- Baseline health service utilisation questionnaire

Acute illness characteristics:

- ICU admission diagnosis
- APACHE II score
- o duration of mechanical ventilation
- o duration of renal replacement therapy (if required)
- SOFA score from the 24hrs period prior to the participant being ready for ICU discharge.

Blood sampling:

- 1. Blood required for cross matching: These samples should follow normal local procedures and are not considered research samples. Only send this sample if not available clinically and required for transfusion.
- 2. Hospital Laboratory (using local sampling volumes and processes): haemoglobin concentration; reticulocyte count; C Reactive Protein (CRP). These results should be collected for all trial participants. Existing results from samples taken <24hrs prior to randomisation can be used. It is acceptable to use the screening haemoglobin as the baseline haemoglobin if from <24 hours prior to randomisation. Use local procedures to 'add on' tests to appropriate existing clinical samples where possible (for example reticulocyte

count and CRP). If not available, the samples should be taken as part of clinical care but if not possible they should be taken as additional research samples.

Refer to section 5.1.3 for guidance on baseline Hb results and study procedures.

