10.4 Reporting SAEs to the Sponsor (ACCORD)

Any AE that is assessed as an SAE is subject to expedited reporting requirements to the Sponsor. The SAEs described in 10.2.1 do not require expedited reporting to the sponsor

The Investigator is responsible for reporting SAEs to ACCORD within 24 hours of becoming aware of the event.

SAE reports will either be emailed as a .pdf file to [contact]; or delivered in person using the Serious Adverse Event Report Form. SAE reports will be complete as far as possible and will be signed and dated by the Investigator. The SAE does not require to maintain blinding as this is an unblinded trial. The Research Governance Coordinator, or designee, will complete and return the Cover Sheet and Return Receipt or send an email to confirm receipt of the SAE report within 1 working day. If this email/fax is not received within 1 working day of sending the report to ACCORD, the Investigator must telephone ACCORD on [name] to check that the report has been received by ACCORD.

All copies of SAE reports emailed or faxed to ACCORD and any follow-up information and correspondence will be kept by the Investigator in the Investigator Site File (ISF) and by the Sponsor in the Sponsor File or Trial Master File (TMF).

ACCORD will report SAEs, as required, to the Chief Investigator/Trial Manager within agreed timelines.

11 SUB-STUDY TO EXPLORE REASONS THAT PATIENTS DECLINE CONSENT TO PARTICIPATE (STUDY WITHIN A TRIAL (SWAT))

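### The recalled SF-36 and the ICU Mobility Scale may be scored after allocation is known, although both are meant to serve as pre-treatment baselines in the primary and moderation analyses

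*Protocol*

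**What the plan says.** **Randomisation.** Protocol section 5.1.3, which deals with haemoglobin during screening, states in scenario (a): "In this situation the patient should be immediately randomised and managed according to the allocated group". Scenario (c)(iii) adds: "Once a patient has provided consent they should be randomised immediately without waiting for further testing".

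**Baseline window.** Section 7.1: "Baseline is the day of randomisation until 23:59 that calendar day". The window therefore includes hours after allocation. The same section says of baseline data that "all data will be extracted from the patient record and apply to the time leading up to randomisation".

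**The two scores.** For the SF-36 recalled for the period before hospitalisation, section 7.2 says: "Attempt to complete as close to the time of enrolment as possible". It continues: "For patients lacking capacity at enrolment, this measure can be deferred until patients regain capacity". The other entry reads: "ICU Mobility Scale (IMS) at the time of randomisation". No section requires either score before allocation, or from an assessor unaware of the arm.

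**Blinding.** Section 10.4 confirms that "this is an unblinded trial". The scientific summary has every intervention patient receive a red cell unit after randomisation, so the arm soon becomes plain to patient and staff.

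**Use in the analysis.** Section 2.3.1 gives the primary endpoint as PCS at 90 days. Section 9.2 writes it as the change in PCS from baseline. Section 9.2 also lists recalled quality of life and the mobility scale among possible adjustment covariates, and names both among its four moderators, alongside comorbidity score and CRP.

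**The concern.** A baseline covariate protects a randomised comparison only if allocation cannot have influenced it. A recalled SF-36 is the patient's own account of earlier health. A patient who already knows whether they will be transfused may judge that earlier state differently, and a member of staff who knows the arm may rate mobility differently.

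Three uses are exposed. In an adjusted model, an arm-related shift in the covariate moves the treatment estimate. In a raw change score, a shift in recalled PCS enters the outcome in full. In the moderation analysis, a score given after allocation no longer describes the patient before treatment. Section 9.2.1 also adjusts SF-6D utilities for baseline values, so the same answers may reach the QALY result.

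This belongs in the protocol because it concerns the order of data collection. No statistical analysis plan can later recover a pre-allocation score that was not taken.

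**Working it through.** **1. Order of events.** Consent leads to immediate randomisation (5.1.3). Baseline stays open until midnight that day (7.1). The SF-36 is to be close to enrolment on either side, and the mobility scale is tied to randomisation without a before or after (7.2). A site can meet all of these rules and still score both instruments after allocation. The sentence in 7.1 on the time leading up to randomisation fixes the period described, not when the answer is given, and a patient's recollection cannot be taken from a record. Section 7.2 does set an order where one was wanted: research blood is to precede transfusion whenever possible. The two scores have no such rule.

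**2. The plan's own figure** (section 9.1: difference 5, SD 12, two-sided 5%, 90% power).
- n per arm = 2 × (1.960 + 1.282)² × 12² / 5² ≈ 121.04, rounded up to 122, so 244 in total, as stated.
- 244 / 0.8 = 305, as stated. 244 / 0.7 = 348.6 against 346 stated, which does not affect this point.
- SE = 12 × √(2/122) = 1.54.

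**3. Bias formulas.** Let d be the between-arm shift in recalled PCS among affected patients, f the share affected, and b the slope of 90-day PCS on recalled PCS.
- Baseline-adjusted model: bias = −b × f × d. This also holds for change from baseline with baseline as a covariate.
- Raw change score: bias = −f × d.
- Type I error = Φ(−1.96 + |bias|/SE) + Φ(−1.96 − |bias|/SE).
- Power if the bias works against the intervention = Φ((5 − |bias|)/SE − 1.96).

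**4. Inputs not in the documents.** b, d and f are assumptions, taken here as b = 0.5 and d = 2. The 15% row borrows the section 5.2 figure for patients who may be delirious at ICU discharge, as a low guide to how many are scored late.

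| Share affected | Adjusted bias (0.5 × 2 × f) | Type I error | Power | Raw-change bias (2 × f) | Type I error |
|---|---|---|---|---|---|
| 15% | 0.15 | 5.1% | 88% | 0.30 | 5.4% |
| 50% | 0.50 | 6.2% | 83% | 1.00 | 10% |
| 100% | 1.00 | 10% | 74% | 2.00 | 25.6% |

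The raw-change columns use the same SE. That is right for equal SDs of 12 and a correlation of 0.5, since 12 × √(2 × (1 − 0.5)) = 12.

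**5. Check.** Simulated baseline-adjusted trials (122 per arm, slope 0.5, 2-point shift, no true effect) gave mean biases of −0.19, −0.50 and −1.01 and rejection rates of 5.1%, 6.3% and 11.4%. The last is a little above 10% because adjustment shrinks the residual SD to 12 × √(1 − 0.25) = 10.4.

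**6. Range.** For d from 1 to 3, b from 0.3 to 1.0 (1.0 being the raw change score) and f from 15% to 100%, the bias runs from 0.15 × 1 × 0.3 = 0.045 to 3.0 points, against the 5-point target difference. No size was worked out for the moderation analyses.

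**The case against.** The case for leaving the text alone is that order of completion may be set in the case report forms or database, which are not shown, and that section 9.2 says only that the covariates may include these scores. The documents do not show that knowing the arm alters recall of health before admission, and an ordinal mobility scale leaves less room for this than a recalled questionnaire. All of that stands as a limit on size. It does not supply the missing timing rule, and recalled PCS is in the endpoint as section 9.2 writes it, whichever covariates are chosen.

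A reader might infer four stronger points that the documents do not support:
- **That section 5.1.3 forbids questionnaires before randomisation.** Every scenario there is about haemoglobin, and the testing not to be waited for is haemoglobin testing. A site may complete the SF-36 between consent and randomisation; it is simply not told to.
- **That the Clinical Frailty Index is equally exposed.** It is collected, but section 9.2 names it neither as a covariate nor as a moderator. It could enter only through the general allowance for strongly prognostic variables.
- **That the Functional Comorbidity Index is equally exposed.** It is a moderator, but section 9.2 describes it as a count of morbidities, which leaves little room for opinion.
- **That a type I error near 10% is to be expected.** With b = 0.5 and d = 2 in the adjusted model, that figure needs every patient to be affected.

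**Conclusion.** The point holds for the recalled SF-36, including in patients with capacity, and for the ICU Mobility Scale. Following the stated timing rules can produce baselines scored with knowledge of the arm in an open trial.

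Under the assumed slope and shift, the adjusted bias is 3%, 10% or 20% of the 5-point target difference when 15%, 50% or 100% of patients are affected. A raw change score doubles these shares. Slope, shift, share and direction are all assumptions, and the bias could favour either arm. The effect is small if only patients lacking capacity are scored late, and material if late scoring is the norm. This is an inexpensive safeguard worth adding, not evidence that the trial's result is compromised.

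**What to change.** - **Section 7.2:** require the recalled SF-36 (in patients with capacity) and the ICU Mobility Scale to be completed after consent and before allocation is revealed.
- **Section 5.1.3:** state that immediate randomisation means not waiting for haemoglobin results, and that it does not displace these two scores.
- **Database:** check that both are entered before the allocation is released, with an override for the SF-36 when capacity is lacking. Store the date and time of each score.
- **Incapacity:** keep the deferral. Setting every late recall to missing would discard baseline data from patients whose inclusion section 5.2 calls important.
- **Analysis:** pre-specify a sensitivity analysis that flags or excludes scores taken after allocation, dropping the score and not the patient. For patients already enrolled, use whatever completion timing is on record.

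The cost is protocol wording, a database check and a short delay on the day of consent. The sample size does not change.
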